- 1) 250 patients recruited from across the following countries (United Kingdom, Sweden, Denmark, Switzerland, Spain, Slovakia and Norway) and up to 100 patients from Germany who are currently using or have filled a prescription for TROBALT at least once in the last 3 months.
- 2) 200 neurologists who have prescribed an anti-epileptic drug (AED) at least once in the last 3 months, and who were on the list to which a letter containing the Physician's Guide for TROBALT was distributed from across the following countries (United Kingdom, Sweden, Denmark, Switzerland, Spain, Slovakia and Norway). At least 75 of the neurologists will have prescribed TROBALT. The survey will also aim to include up to 100 neurologists from Germany of which approximately 50 will have prescribed TROBALT.

Patients eligible for the survey will be asked to take the survey online or via a telephone interview if the latter is preferred. Neurologists will be invited to take the survey online.

The selected countries were the first five countries to launch TROBALT (Germany, Denmark, United Kingdom, Switzerland and Sweden) and an additional three countries with launch in 2011, but with relatively high rates of uptake of TROBALT (Spain, Slovakia and Norway). The selection of countries includes Switzerland, which is not part of the European Union. However, the key messages regarding the risks with TROBALT are in alignment. The rationale for surveying the first five countries to launch is so that any issues identified from these countries regarding the effectiveness of the Physician's Guide and PIL in communicating the risks of TROBALT can be addressed as soon as possible, and the key messages can be revised in a timely manner. In addition, these countries are likely to provide the greatest number of neurologists with experience of prescribing TROBALT, and their patients.

Study Endpoints/Assessments

The primary outcome of the survey is the proportion of patients/neurologists providing correct responses to a series of questions concerning the significant risks associated with TROBALT. The risks evaluated will be those described in the TROBALT PIL and in the Physician's Guide.

1. INTRODUCTION

GlaxoSmithKline (GSK) will conduct a survey of patients' understanding of the significant risks associated with TROBALT™ (retigabine). The survey will concentrate on the risks described in the approved EU Patient Information Leaflet (PIL) for TROBALT, though it is recognised that the PIL is not the only source of information concerning risks associated with medication use.

GSK will also survey neurologists who are prescribing anti-epileptic drugs (AEDs) on their understanding of the significant risks associated with TROBALT. Neurologists were chosen as the target HCPs because all neurologists in each country to be surveyed were sent a letter containing the Physician's Guide and SmPC at the launch of TROBALT in that country (Appendix 1). Neurologists were targeted for this letter on the basis that they constituted the broadest group that were reasonably likely to initiate a prescription of TROBALT. Furthermore, a sub-group of neurologists commonly referred to as 'epileptologists' are known from past experience to be the specialists who first initiate prescriptions of a new AED and were therefore specifically targeted for promotional activity by GSK and are the primary target of this survey. The survey will concentrate on the risks described in the Physician's Guide for TROBALT, though it is recognised that the Physician's Guide is not the only source of information concerning risks associated with medication use.

The design for this study is based on GSK's previous experience designing risk management programs for GSK products, and on the prior experience of [REDACTED] Corporation ([REDACTED]) in conducting similar surveys in the EU.

2. OBJECTIVE(S)

The objectives of this study are:

1. To assess patients' understanding of the significant risks associated with TROBALT as evaluated by a survey instrument.
2. To assess prescribers' understanding of the significant risks associated with TROBALT as evaluated by a survey instrument, for those who should have received the letter containing TROBALT Physician's Guide, and specifically for the subset of prescribers who have prescribed TROBALT.

3. INVESTIGATION PLAN

3.1. Study Design

This study is sponsored by GlaxoSmithKline (GSK), and will be conducted by [REDACTED] an international research consultancy.

This is a cross-sectional study of physicians' and patients' understanding of the significant risks associated with TROBALT.

Physicians will be recruited by selecting a random sample of neurologists from lists provided by GSK in each country. The list includes names of all potential TROBALT prescribers who were mailed an introductory letter including the Physician's Guide for TROBALT (Appendix 1). Following recruitment, neurologists' understanding of the potential risks associated with TROBALT will be evaluated using an online survey. Each invitation will include information on how to access the survey on-line, and will include a unique code to ensure that the invitation is used only once.

The primary method of recruiting patients is through their physicians. In countries in which a list of current TROBALT prescribers can be obtained, a random sample of prescribers in each country will be selected. Otherwise, the sample will come from the list of neurologists who were mailed the Physician's Guide, who have not participated in the neurologist survey. Sampled prescribers will be asked to provide survey invitations to their patients being treated with TROBALT. Each prescriber will be given 10 invitations and asked to provide these invitations to up to 10 consecutive patients who have been prescribed TROBALT in the last 3 months. If the patient response rate using this recruitment method is lower than expected, then other options will be identified including patient panels where available.

Following recruitment, patients' understanding of the potential risks associated with TROBALT will be evaluated using an online survey or the same survey instrument delivered during a telephone interview. The latter option aims to accommodate individuals who are not comfortable with online technology or are not computer literate. Each invitation will include information on how to access the online survey and will also provide the toll-free number for accessing the Survey Call Centre.

To ensure comprehension of each communication piece, all of the physician and patient outreach will be conducted in the local country language. Specifically, the surveys and invitation letters will all be translated by a certified translation company. In addition, when conducting the survey by telephone, the person conducting the survey will be a native language speaker.

3.2. Study Populations

3.2.1. Patients using TROBALT

This survey aims to recruit 350 patients who are currently being treated with TROBALT or who have received TROBALT within the last 3 months. These numbers reflect a trade-off between what is practical in terms of recruitment, given the relatively low predicted uptake of TROBALT, and providing sufficient precision around outcome estimates (proportion giving correct responses per question) (Section 8).

The selected countries were the first five countries to launch TROBALT (Germany, Denmark, United Kingdom, Switzerland and Sweden) and an additional three countries with launch in 2011, but with relatively high rates of uptake of TROBALT (Spain, Slovakia and Norway). The selection of countries includes Switzerland, which is not part of the European Union. However, the key messages regarding the risks with TROBALT are in alignment. The rationale for surveying the first five countries to launch is so that any issues identified from these countries regarding the effectiveness of the Physician's

Guide and PIL in communicating the risks of TROBALT can be addressed as soon as possible, and the key messages can be revised in a timely manner. In addition, these countries are likely to provide the greatest number of neurologists with experience of prescribing TROBALT, and their patients.

Two-hundred fifty patients will be recruited from across the following countries (United Kingdom, Sweden, Denmark, Switzerland, Spain, Slovakia and Norway). If required, additional EU countries may be included in the survey to reach the minimum recruitment target. Up to one hundred patients will be recruited from Germany, which was one of the earliest countries to launch and currently has the highest volume of use of TROBALT in Europe. However, it should be noted that on May 31, 2012, following the reimbursement process in Germany, GSK chose not to enter into price negotiations and TROBALT will not be available for new patients from July 2012 until further notice. Patients currently on TROBALT prior to May 31, 2012 will continue to be able to fill their TROBALT prescriptions in Germany. Therefore, by November 2012 at the start of the survey, the characteristics of the patients using TROBALT in Germany may differ from the other European countries where new patients will continue to receive TROBALT prescriptions. Additionally, the neurologists included from Germany will only be those who continue to prescribe TROBALT, and this may be a selected population. For these reasons, the survey data from Germany will be analysed with the total study population, as well as separately.

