3.2.2. Neurologists prescribing anti-epileptic drugs

This survey aims to recruit a random sample of 300 neurologists prescribing AEDs and who have been sent the TROBALT Physician's Guide. A sample of 200 neurologists will be recruited from across the following countries (United Kingdom, Sweden, Denmark, Switzerland, Spain, Slovakia and Norway), and up to 100 neurologists will be recruited from Germany. If required, additional EU countries may be included in the survey to reach the minimum recruitment target. The recruitment will be from among those who have prescribed an anti-epileptic drug (AED) at least once in the last 3 months, and who were on the list to which a letter including the Physician's Guide TROBALT was distributed. The survey will aim to recruit at least 75 physicians (from the seven specified countries) and 50 physicians from Germany with experience of prescribing TROBALT for sub-analyses, as these individuals would be expected to be more aware of the risks of TROBALT. The sub-group of neurologists commonly referred to as 'epileptologists' are known from past experience to be the specialists who first initiate prescriptions of a new AED and were therefore specifically targeted for promotional activity by GSK and are the primary target of this survey.

As with the patient population, these numbers reflect a trade-off between what is practical in terms of recruitment, given the relatively low predicted prescribing of TROBALT, and providing sufficient precision around outcome estimates (proportion giving correct responses per question), and also to allow analysis of the sub-sample of neurologists who have prescribed TROBALT.

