4.2. Neurologist Screening and Assessment

The health care provider introduction information is outlined in Appendix 4, and the survey instrument for neurologist assessment is in Appendix 5. The neurologist questionnaire will begin with a screening module with questions to confirm eligibility. Depending on the answers to the screening questions, survey participation could either be terminated or continued. If ineligible, the respondent is immediately notified with a “thank you” message that survey participation has ended. If eligible, the respondent is allowed to continue survey participation.

The screening questions included in the prescriber survey are:

- Agreement to take the survey
- Time since the last prescription written for any AED
- Ever prescribe TROBALT*
*Used to ensure that the sample includes at least 100 TROBALT prescribers
- Employment at GSK or [REDACTED]

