The sample of neurologists who are invited to participate will be a random sample of all neurologists who received the Physician's Guide for TROBALT. The sample of participating neurologists will be self-selected since respondents will voluntarily respond to the invitation to participate; however, the survey recruitment strategies are intended to recruit a heterogeneous sample of prescribers for participation. For Germany, as noted in section 3.2.1, TROBALT will no longer be available for new patients and so only neurologists who continue to have patients on TROBALT in November 2012 will be targeted.

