The information in this survey and the Patient Information Leaflet (PIL) should not take the place of talking with your health care professional. If you have any questions about your condition or treatment, or if you would like more information about TROBALT, talk to your health care professional. The Patient Information Leaflet can be obtained from the following website: <http://www.gsk.com/products/prescription-medicines/trobalt.htm>.

Thank You

Appendix 5 Questionnaire for Neurologists who Prescribe AEDs and were Sent the TROBALT Letter Containing the Physician's GuideScreening Questions:

1. Do you agree to take part in this survey?
 - **Yes**
 - No (Exclude)

2. When was the last time you prescribed an anti-epileptic drug for a patient?
 - **Less than a month ago**
 - Between 1 and 2 months ago
 - Between 2 and 3 months ago
 - More than 3 months ago (Exclude)

3. Have you ever prescribed TROBALT?
 - **Yes**
 - No
 - I don't know

4. In which country is your primary medical practice?
 - **Germany**
 - Denmark
 - United Kingdom
 - Switzerland
 - Sweden
 - Spain
 - Slovakia
 - Norway
 - Other (exclude)

[QUOTAS WILL BE ESTABLISHED FOR 200 NEUROLOGISTS FROM UK, SWEDEN, DENMARK, SWITZERLAND, SPAIN, SLOVAKIA, AND NORWAY; AT LEAST 75 SHOULD HAVE PRESCRIBED TORBALT. QUOTA OF 100 NEUROLOGISTS FROM GERMANY, OF WHICH AT LEAST 50 SHOULD HAVE PRESCRIBED TROBALT.]

5. Are you an employee of GlaxoSmithKline or [REDACTED] Corporation?
 - **Yes (Exclude)**
 - **No**

Questionnaire for Neurologists who Prescribe AEDs and Were Sent the TROBALT Letter Containing the Physician's Guide

[CORRECT ANSWERS ARE INDICATED IN BOLD]

6. For which of the following conditions is TROBALT approved for use?
- Migraine
 - **Partial-onset seizures**
 - All types of seizures
 - All of the above
 - None of the above
 - I don't know
7. Is TROBALT indicated for use as monotherapy?
- Yes
 - **No**
 - I don't know
8. What is the maximum recommended daily maintenance dose of TROBALT for most patients? (Please select the best response.)
- 600 mg
 - 900 mg
 - **1200 mg**
 - 2000 mg
 - None of the above
 - I don't know
9. Which one of the following statements is true? (Please select the best response.)
- TROBALT should be taken once a day.
 - TROBALT should be taken twice a day.
 - **TROBALT should be taken three times a day.**
 - TROBALT should be taken four times a day.
 - None of the above
 - I don't know

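### The German neurologist sample is defined in two incompatible ways: continuing TROBALT prescribers only, or up to 100 neurologists of whom about half have prescribed it

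*Protocol*

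**What the plan says.** **Restricted to continuing users.** Section 3.2.1, after explaining that TROBALT is closed to new German patients from July 2012, says that "the neurologists included from Germany will only be those who continue to prescribe TROBALT" and that this may be a selected group. Section 8, in the paragraph on neurologists invited to take part, says that for Germany "only neurologists who continue to have patients on TROBALT in November 2012 will be targeted".

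**Mixed sample.** The Protocol Summary aims for "up to 100 neurologists from Germany of which approximately 50 will have prescribed TROBALT". Section 3.2.2 describes a random sample of 300 AED prescribers who were sent the Physician's Guide, 200 from seven countries and up to 100 from Germany, with "at least 75 physicians (from the seven specified countries) and 50 physicians from Germany with experience of prescribing TROBALT for sub-analyses". The inclusion criteria in Section 3.2.2.1 are an AED prescription in the last 3 months and presence on the mailing list, with nothing specific to Germany. The quota note at Question 4 of Appendix 5 reads "QUOTA OF 100 NEUROLOGISTS FROM GERMANY, OF WHICH AT LEAST 50 SHOULD HAVE PRESCRIBED TROBALT".

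**Overall prescriber count.** A footnote in Section 4.2 says of the question on ever prescribing TROBALT: "Used to ensure that the sample includes at least 100 TROBALT prescribers".

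**Reporting.** Sections 6.1.2 and 6.2.2 call for results for all eight countries, for Germany alone and for the seven other countries, plus a separate summary for neurologists who have ever prescribed TROBALT.

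**The concern.** The two descriptions lead to different invitations in Germany. Under the restricted one, essentially every German respondent has prescribed TROBALT. Under the mixed one, about half have not.

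Objective 2 has two limbs: neurologists who should have received the letter, and specifically those among them who have prescribed TROBALT. A restricted German sample serves only the second. There would be no German non-prescribers, the German prescriber table would repeat the German table, and the eight-country result would combine a prescriber-only sample from one country with a general AED-prescriber sample from seven.

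Section 3.2.2 expects prescribers to be more aware of the risks. By the protocol's own reasoning, then, the restricted frame would raise the measured knowledge and flatter the educational plan under evaluation. Once invitations have gone out, analysis cannot recover a frame that was not sampled.

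**Working it through.** **1. The sections side by side.**

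| Place in the protocol | German neurologists | Fits a continuing-prescriber sample? |
|---|---|---|
| Section 3.2.1 | continuing prescribers only | is the restriction |
| Section 8 | only those with patients on TROBALT in November 2012 | is the restriction, in near-identical terms |
| Summary | up to 100, approximately 50 prescribers | no |
| Sections 3.2.2 and 3.2.2.1 | mailing-list AED prescribers, no German exception | restriction not stated |
| Appendix 5, Question 4 note | 100, at least 50 prescribers | yes, but the minimum never binds |

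Under the Section 3.2.1 wording every respondent is an ever-prescriber by definition. Under the Section 8 wording this is so in practice, since these neurologists have patients on the drug.

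**2. The plan's own totals.** The sample size reproduces: 200 + 100 = 300. The prescriber floor in Section 4.2 (100) is not the sum of the regional figures: 75 + 50 = 125.

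**3. Prescriber share of the pooled sample**, with 100 German respondents and 75 prescribers among the other 200:

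- Mixed German sample: (75 + 50)/300 = 125/300 = 41.7%.
- Restricted German sample: (75 + 100)/300 = 175/300 = 58.3%.

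**4. Effect on the estimates.** Let d be the gap in percent correct between prescribers and non-prescribers. With simple pooling, the percent correct is the non-prescriber value plus (prescriber share × d).

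- Pooled shift: (175 − 125)/300 × d = d/6.
- German shift: (100 − 50)/100 × d = d/2.
- Seven-country shift: 0, because Germany is not in that table.

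The protocol gives no value for d, so a range is assumed:

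| Assumed d (points) | Pooled shift | German shift |
|---|---|---|
| 10 | +1.7 | +5 |
| 20 | +3.3 | +10 |
| 30 | +5.0 | +15 |

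For scale, Table 1 in Section 7 gives a margin of ±5.7 points at n = 300 and ±10 at n = 100, both at 60% correct.

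**5. If the restricted frame fills only 50 German places.** Prescribers are then (75 + 50)/250 = 50%. Against 41.7% the pooled shift is d/12: +0.8, +1.7 and +2.5 points for the same three gaps. The German shift stays d/2.

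**6. Precision of the prescriber subgroup** at 50% correct: 1.96 × √(0.25/100) = ±9.8 points with 100 prescribers, and 1.96 × √(0.25/125) = ±8.8 with 125.

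**The case against.** **Section 3.2.1 is the patient section**, so its sentence might mean only the doctors who recruit patients. That does not stand. Section 8 applies the restriction to neurologists invited to the survey and refers back to Section 3.2.1, and Section 6.1.2 relies on the reasons in 3.2.1 to split the neurologist results.

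**The selection is disclosed and Germany is reported separately.** This stands in good part. A seven-country result and a prescriber result are always available, and a restricted German sample still serves the second limb of Objective 2. But disclosure does not tell the field team whom to invite, and the German and pooled tables still have no settled meaning.

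A reader might also infer more than the documents support:

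- *That the Appendix 5 quota is contradicted.* It is not: 100 prescribers out of 100 meets a minimum of 50. Section 3.2.2 can likewise be read as setting minimums. Only the Summary's approximate figure is numerically incompatible with the restriction.
- *That the restriction cannot be applied because the screener asks only about ever prescribing.* Mailing-list membership is not asked in the screener either; it is applied through the invitation list. The German restriction could be applied in the same way.
- *That 100 prescribers in Section 4.2 contradicts 125.* It is worded as a floor, which 125 or 175 would meet, and nothing in the protocol stops recruitment at 100.
- *That the pooled result is biased by 5 points.* That figure needs an assumed 30-point gap and 100 German respondents. Each pooled shift in the range shown is below the Table 1 margin of 5.7 at n = 300 and 60% correct.

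**Conclusion.** The concern holds as an inconsistency about who is sampled in Germany. Sections 3.2.1 and 8 cannot be met together with the Summary, and Sections 3.2.2 and 3.2.2.1 describe the wider frame without the restriction.

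The consequence is largest for the German table (half the prescriber/non-prescriber gap), smaller for the eight-country table (one sixth of it with 100 German respondents, one twelfth with 50) and nil for the seven-country table. These fractions assume simple pooling, 75 prescribers among the other 200, and the same percent correct for continuing as for other prescribers. The shifts in points rest on assumed gaps; only the direction has support in the protocol.

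The Section 4.2 floor is secondary. It is compatible with the regional figures but does not secure them: 100 is reached by 75 + 25 or by 50 + 50, each with a regional target missed.

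**What to change.** Define the German neurologist frame once, before invitations go out, and align the Summary, Sections 3.2.1, 3.2.2, 3.2.2.1 and 8, and the Appendix 5 quota note. Either route works:

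- **(a) Common frame.** Use the same mailing-list and AED criteria in Germany as elsewhere, with the quota of 100 including at least 50 ever-prescribers. Remove the restricting sentences from Sections 3.2.1 and 8. Keep the separate German reporting, and reword its rationale, since Section 6.1.2 now points to Section 3.2.1.
- **(b) Prescriber-only frame.** Keep the restriction and state it in Section 3.2.2.1 as a Germany-specific inclusion criterion, applied through the invitation list or a screener item. Drop the 50-of-100 quota. Label the German and pooled results as including a prescriber-only German sample, and name the seven-country result as the estimate for all neurologists sent the letter.

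In Section 4.2, replace the floor of 100 with the sum of the regional minimums: 125 under (a), or 75 plus the German sample (up to 175) under (b).

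Route (a) costs wording only. Route (b) adds an inclusion criterion, possibly one screener question, and table labels under Sections 6.1.2 and 6.2.2. Neither needs respondents beyond the numbers already planned, though under (b) fewer than 100 eligible German neurologists may be found.
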